- Definite relevance: The adverse event is clearly related to the investigational agent. For example, an event that follows a reasonable temporal sequence from administration of the study intervention abides by a known or expected response pattern to the suspected intervention, which improves by stoppage and reappears through repeated exposures, but is unable to be reasonably explained by the known characteristics of the subject's clinical state;
- Possible relevance: An adverse event that follows a reasonable temporal sequence from administration of the study intervention abides by a known or expected response pattern to the suspected intervention, which can be easily induced by various other factors;
- Irrelevance: The adverse event is clearly uncorrelated with the research agent or procedure. For example, there exists another plausible cause, and/or a clinically plausible temporal sequence is inconsistent with the onset of the event and the study intervention and/or a causal relationship is considered biologically implausible.

Serious adverse event:

A serious adverse event (SAE) event is defined as the event with one of the following consequences:

- Death;
- Life-threatening condition;
- Hospitalization or extension of hospitalization;
- Temporary or permanent disability;
- Congenital anomaly or malformation;

-
- Important medical events: although the event caused by the drug which may endanger the subjects may not be life-threatening and result in death or require hospitalization, medical or surgical intervention requires to be taken to prevent one of the outcomes based on the appropriate medical judgment.

Definition of an unexpected adverse event:

An unexpected adverse event of the product is defined as the event with the nature, severity or course non-corresponding to the product information mentioned in the summary when it is authorized or in the investigator's brochure when it is not authorized.

Expected adverse events:**➤ Due to myelosuppression**

Neutropenia related infections, fever;

Bleeding: ecchymosis, petechial, haematemesis, hemoptysis, melena, hematuria, etc;

Weary, somnolence, pale, etc (due to anemia);

➤ Due to other non-hematological toxicity

Liver dysfunction;

Renal dysfunction;

➤ Related to the haematological disease

Death

Relapse of any kind

➤ Related to drug allergy

Erythra, edema, pruritus, swelling, etc.

Procedures of all adverse event

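### The relatedness scale has no level for a new toxicity of uncertain cause and two levels for a confounded event, and the expected-event list containing Death is not reconciled with the definition of unexpected

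*Combined protocol and SAP*

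**What the plan says.** The relevant text lies in the adverse-event part of the protocol.

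- **Relevance, Definite.** The rule and the start of its illustration read: "The adverse event is clearly related to the investigational agent. For example, an event that follows a reasonable temporal sequence". The illustration goes on to a known or expected pattern, an event "which improves by stoppage and reappears through repeated exposures", and the lack of a reasonable explanation in the patient's clinical state.
- **Relevance, Possible.** The timing must be reasonable and the event must be one that "abides by a known or expected response pattern to the suspected intervention, which can be easily induced by various other factors". Nothing marks these features as an example; they are the definition.
- **Relevance, Irrelevance.** The rule is that the event is clearly uncorrelated with the study agent or procedure. The illustration begins "For example, there exists another plausible cause" and is joined by and/or to implausible timing and biological implausibility, so each can stand alone.
- **Definition of an unexpected adverse event.** The test is nature, severity or course "non-corresponding to the product information mentioned in the summary when it is authorized", or the investigator's brochure if the product is not authorised.
- **Expected adverse events.** There are four groups: myelosuppression, other non-haematological toxicity, the disease, and drug allergy. The group "Related to the haematological disease" holds two entries, Death and "Relapse of any kind".
- **Procedures of all adverse event; Monitoring committee.** Every adverse event is recorded whatever its severity or presumed relationship, and the investigator enters an opinion on the relationship in the eCRF. Serious events go on their own form. Three independent people review overall mortality and serious adverse events.

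**The concern.** A relatedness scale should give every event exactly one level. This one appears to fail in both directions: some events fit no level and others fit two. The events without a level are new toxicities of uncertain cause. A study of five drugs given together, with safety in its primary objective, should be able to place them.

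The design is single-arm, so there is no control rate against which excess toxicity could be seen. What counts as treatment-related rests on the investigator's rating. The Statistical methods section names only a Kaplan-Meier estimate of 1-year survival and no safety analysis, so nothing later in the plan would correct a wrong rating.

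The expected-event list raises a second question. Death is an outcome and relapse is a failure of efficacy. Listing them as expected adverse events invites the reader to treat a death as expected before its cause has been settled.

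**Working it through.** No arithmetic applies; the check is to run typical events through the definitions as written.

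**Relatedness.** All four events below have plausible timing.

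| Event | Definite | Possible | Irrelevance | Result |
|---|---|---|---|---|
| Known pattern, other factors could also cause it | Not unless clearly related | Yes | Meets the example of another plausible cause | Two levels |
| No known pattern, cause uncertain | No, not clearly related | No, lacks the pattern | No, not clearly uncorrelated | No level |
| No known pattern, judged clearly related | Yes | No | No | One level |
| Known pattern, no other likely cause, no re-exposure, judged clearly related | Yes | No, other factors are required | No | One level |

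1. The second row is the gap. If such an event also has some other plausible cause, the only wording it matches is the example under Irrelevance. A rater who works from the example would then call it unrelated, although the rule above that example is not met.
2. The first row is the overlap. Possible requires that other factors could produce the event; Irrelevance offers another plausible cause as sufficient illustration. In relapsed or refractory AML, the disease or an infection will often be a plausible alternative. The line between related and unrelated is then left to the individual rater.

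**Expectedness.** Take a fatal toxicity that no product summary or brochure describes.

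1. By the definition, it is unexpected, because nature and severity both count.
2. By the list, Death is expected. The only qualifier is the disease heading above it.
3. That heading helps only once the death has been attributed. The protocol gives no instruction to record a cause of death, and the attribution would use the scale examined above.
4. The protocol does not say whether the definition or the list governs. The definition also speaks of one product, while Dosage and administration names five: azacytidine, the PD-1 inhibitor, homoharringtonine, cytarabine and G-CSF.
5. The list is not a complete reference in any case. It names no immune-related event, although the Background cites an 11% rate at grade 3-4 with a PD-1 inhibitor plus azacytidine.

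**The case against.** The strongest reply is that nothing is lost. Every adverse event is recorded regardless of presumed relationship, death is always a serious adverse event, and the independent committee sees overall mortality and serious events, not only those rated related or unexpected. No reporting, review or analysis step is expressly conditional on relatedness or expectedness, and no treatment-related-mortality endpoint is defined. This stands, and it limits the point to how events are labelled.

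Three stronger readings are tempting, and the documents do not support them.

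- A reader might infer that only events with a known pattern can be rated as related. Under Definite, the pattern, improvement on stopping and recurrence on re-exposure appear only as an example. A new event, a fatal event or one without re-exposure can be Definite if judged clearly related.
- A reader might infer that a fatal toxicity can never be unexpected, or that the list contradicts the definition. The definition still captures a fatal toxicity that the product information does not describe, and Death stands under a disease heading, apart from the drug-toxicity groups. The two texts are unreconciled rather than contradictory.
- A reader might try to size the problem from 30 patients and the 6.3-month median survival in the Background. That median belongs to a different regimen, and many of the deaths would properly be due to disease. Neither a count of deaths nor the chance of seeing a toxicity measures how often an event is mislabelled.

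It is also fair to say that a fourth, probable level is a matter of preference, and that listing relapse as foreseeable does not remove it from the efficacy assessment.

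**Conclusion.** The point holds as a defect of classification. Possible is defined so that a plausibly timed new toxicity of uncertain cause has no level, and Possible and Irrelevance overlap whenever another cause is plausible. Death and relapse are listed as expected with no statement of how the list relates to the product-information test, so a fatal toxicity risks being called expected by default.

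The consequence is misattribution in the safety results, not missing events, and it does not touch the response endpoint. Its size cannot be given: the documents contain no rate of uncertain or confounded events and no guide to how raters would resolve them. The conclusion rests on reading the Possible definition as a set of joint requirements, which is what its wording supports. The change is worth making because safety is half of the primary objective and there is no comparator arm.

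**What to change.** Amend the wording and the matching eCRF code lists:

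1. **Possible:** timing is reasonable, the event is not clearly related, and one or more study drugs cannot be excluded as a cause. A known pattern supports the rating but is not required, and another possible cause neither qualifies nor disqualifies the event.
2. **Irrelevance:** only events for which a study-drug cause is excluded, for instance by timing. Another plausible cause alone is not enough. With Definite kept as clearly related, the three levels are then exhaustive and do not overlap. A probable level is optional.
3. **Expected list:** remove Death and relapse, or limit them to events attributed to the leukaemia.
4. **Deaths:** record death as the outcome of a named event, with its cause coded as disease, treatment or other.
5. **Expectedness:** state that it is judged only by the product information or investigator's brochure, and name that document for each of the five drugs. Check the absence of immune-related events from the list against it.

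The cost is a protocol amendment with ethics committee approval, the code-list change, and re-rating of any events already coded. Somewhat more events will be rated related or unexpected, so the safety tables will look less favourable.

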Appendix

Appendix 1. ECOG score

Appendix 2. NCCN Guidelines Version 2.2020 Acute Myeloid Leukemia

Appendix 3. Patient consent form for study participation

Appendix 1. ECOG score*

Grade	Performance status
0	Fully active, able to carry on all pre-disease performance without restriction.
1	Able to move freely and take mild physical activity, such as housework and office work, but restricted in severe physical activity.
2	Able to move freely and take care of himself, but loss of work capability; doing activities for more than half of the waking hours.
3	Capable of taking care of himself partially, confined to the bed or chair for more than half of the waking hours.
4	Completely disabled, unable to take care of himself and totally confined to the bed or chair.
5	Dead

Notes: ECOG=Eastern Cooperative Oncology Group; * Oken M, Creech R, Tormey D, et al. Toxicity and response criteria of the Eastern Cooperative Oncology Group. Am J Clin Oncol. 1982;5:649-655.

Appendix 2.NCCN Guidelines Version 2.2020 Acute Myeloid Leukemia

RISK STRATIFICATION BY GENETICS IN NON-APL AML^{1,2}

Risk Category*	Genetic Abnormality
Favorable	t(8;21)(q22;q22.1); RUNX1-RUNX1T1 inv(16)(p13.1;q22) or t(16;16)(p13.1;q22); CBFB-MYH11 Biallelic mutated CEBPA Mutated NPM1 without FLT3-ITD or with FLT3-ITD ^{low†}
Intermediate	Mutated NPM1 and FLT3-ITD ^{high†} Wild-type NPM1 without FLT3-ITD or with FLT3-ITD ^{low†} (without adverse-risk genetic lesions) t(9;11)(p21.3;q23.3); MLL3-KMT2A ‡ Cytogenetic abnormalities not classified as favorable or adverse
Poor/Adverse	t(6;9)(p23;q34.1); DEK-NUP214 t(v;11q23.3); KMT2A rearranged t(9;22)(q34.1;q11.2); BCR-ABL1 inv(3)(q21.3q26.2) or t(3;3)(q21.3;q26.2); GATA2,MECOM(EVI1) -5 or del(5q); -7; -17/abn(17p) Complex karyotype,§ monosomal karyotype Wild-type NPM1 and FLT3-ITD ^{high†} Mutated RUNX1 ¶ Mutated ASXL1 ¶¶ Mutated TP53 #

¹ Döhner H, Estey E, Grimwade D, et al. Diagnosis and management of AML in adults: 2017 ELN recommendations from an international expert panel. *Blood* 2017;129:424-447.

² Frequencies, response rates, and outcome measures should be reported by risk category, and, if sufficient numbers are available, by specific genetic lesions indicated.

* Prognostic impact of a marker is treatment-dependent and may change with new therapies.

† Low, low allelic ratio (<0.5); high, high allelic ratio (≥0.5); semiquantitative assessment of *FLT3-ITD* allelic ratio (using DNA fragment analysis) is determined as ratio of the area under the curve "*FLT3-ITD*" divided by area under the curve "*FLT3-wild type*"; regardless of *FLT3* allelic fractions, patients should be considered for hematopoietic stem cell transplant, though recent studies indicate that AML with *NPM1* mutation and *FLT3-ITD* low allelic ratio may also have a more favorable prognosis and patients should not routinely be assigned to allogeneic HCT. *FLT3* allelic ratio is not yet pervasively used, and IF not available, the presence of an *FLT3* mutation should be considered high risk unless it occurs concurrently with an *NPM1* mutation, in which case it is intermediate risk. As data emerge, this measure will evolve.

‡ The presence of t(9;11)(p21.3;q23.3) takes precedence over rare, concurrent adverse-risk gene mutations.

§ Three or more unrelated chromosome abnormalities in the absence of 1 of the WHO-designated recurring translocations or inversions, that is, t(8;21), inv(16) or t(16;16), t(9;11), t(v;11)(v;q23.3), t(6;9), inv(3) or t(3;3); AML with *BCR-ABL1*.

|| Defined by the presence of 1 single monosomy (excluding loss of X or Y) in association with at least 1 additional monosomy or structural chromosome abnormality (excluding core-binding factor AML).

¶ These markers should not be used as an adverse prognostic marker if they co-occur with favorable-risk AML subtypes.

TP53 mutations are significantly associated with AML with complex and monosomal karyotype.

Note: All recommendations are category 2A unless otherwise indicated.

Clinical Trials: NCCN believes that the best management of any patient with cancer is in a clinical trial. Participation in clinical trials is especially encouraged.

RESPONSE CRITERIA DEFINITIONS FOR ACUTE MYELOID LEUKEMIA¹

- **Morphologic leukemia-free state**
 - ▶ Bone marrow <5% blasts in an aspirate with spicules
 - ▶ No blasts with Auer rods or persistence of extramedullary disease
- If there is a question of residual leukemia, a bone marrow aspirate/biopsy should be repeated in one week.
- A bone marrow biopsy should be performed if spicules are absent from the aspirate sample.
- **Complete response (CR)**
 - ▶ **Morphologic CR - patient independent of transfusions**
 - ◊ Absolute neutrophil count >1000/mcL (blasts <5%)
 - ◊ Platelets ≥100,000/mcL (blasts <5%)
 - ◊ No residual evidence of extramedullary disease
 - ▶ **Cytogenetic CR - cytogenetics normal (in those with previously abnormal cytogenetics)**
 - ▶ **Molecular CR - molecular studies negative²**
 - ▶ **CRi - There are some clinical trials that include a variant of CR referred to as CRi. This has been defined as <5% marrow blasts, either ANC <1000/mcL or platelets <100,000/mcL, and transfusion independence but with persistence of cytopenia (usually thrombocytopenia).**
 - ▶ Responses less than CR may still be meaningful depending on the therapy.
- **Partial remission³**
 - ▶ Decrease of at least 50% in the percentage of blasts to 5% to 25% in the bone marrow aspirate and the normalization of blood counts, as noted above.
- Relapse following CR is defined as reappearance of leukemic blasts in the peripheral blood or the finding of more than 5% blasts in the bone marrow, not attributable to another cause (eg, bone marrow regeneration after consolidation therapy) or extramedullary relapse.
- **Induction failure - Failure to attain CR following exposure to at least 2 courses of intensive induction therapy (2 cycles of 7+3 or one cycle of 7+3 and one cycle of HiDAC).⁴**

¹ Cheson BD, Bennett JM, Kopecky KJ, et al. Revised recommendations of the international working group for diagnosis, standardization of response criteria, treatment outcomes, and reporting standards for therapeutic trials in acute myeloid leukemia. *J Clin Oncol* 2003;21(24):4642-4649.

² This is clinically relevant only in APL and Ph+ leukemia at the present time. Molecular remission for APL should be performed after consolidation, not after induction as in non-APL AML.

³ Partial remissions are useful in assessing potential activity of new investigational agents, usually in phase I trials.

⁴ Döhner H, Estey E, Grimwade D, et al. Diagnosis and management of AML in adults: 2017 ELN recommendations from an international expert panel. *Blood* 2017;129:424-447.

Note: All recommendations are category 2A unless otherwise indicated.

Clinical Trials: NCCN believes that the best management of any patient with cancer is in a clinical trial. Participation in clinical trials is especially encouraged.
